7.4 Post-intervention Activities

- Feasibility and Acceptability Data Collection: Semi-structured interviews with participating dentists, CHWs, and other non-patient participants will be conducted (see section 8.1.3)
 - Feasibility Data Collection: EHR data will be reviewed to assess feasibility
-

7.5 Knowledge Modeling Activities

- Create the interview guide for non-patient participant input into the modeling (pre-intervention)
 - Conduct initial non-patient participant interviews to inform model development
 - Conduct the group model-building workshop
 - Conduct follow-up non-patient participant interviews to clarify assumptions
-

8 STUDY PROCEDURES /EVALUATIONS

8.1 Study Procedures/Evaluations

8.1.1 *Workflow analysis*

The team will conduct a workflow analysis, adapted from the Agency for Healthcare Research and Quality (AHRQ) recommendations on workflow assessments, which includes:

1. Direct entry of patient demographic and appointment (site) information into the EHR by patient service representatives (PSRs) or other authorized users;
2. Ability to scan patient medical history (plus baseline oral health measures of self-reported receipt of a dental visit in the past year and brushing with fluoride toothpaste as recommended) directly into a designated SCREENING folder, followed by transcription and review by faculty dentists;
3. MiFi (Wi-Fi hotspot) configuration to each specific laptop (electronic tablet) that will only allow EHR access to the matching laptop (tablet);
4. Multiple layers of security embedded to comply with all applicable policies;
5. Dual authentication process through Citrix via NYU active directory followed by login to the EHR via NYU ID card;
6. Direct entry of screening results into the EHR by dentists; and
7. Customized walkout statements for interview patient participants with screening results and follow-up notes.

A matrix will be created with 3 categories: people, documents, and information content. The group adaptation session will be guided by a user-centered design facilitation protocol that sequentially leads the group through presentation of specific remote EHR use cases that include variations on the original EHR data entry screens adapted to the workflow characteristics of local community sites. For each presented use case, the group discussion will focus on the workflow at the site around the role responsibilities (people), documents, and information content (patient medical history, self-reported outcome measures, head and neck / oral examination results) with regard to reviewing customized EHR protocols based on the findings. The discussion will be digitally recorded and each non-patient participant will be given color-coded response sheets to record their perspectives on how to enhance the usefulness of the customized EHR protocols within the community outreach site setting. The digital recordings and response sheets will then be processed, summarized, and converted into adaptation recommendations by the study team. Next, the study team will transform the recommendations into proposed revisions and document them in revised standard

workflow diagrams that build on established workflows to minimize changes at the sites or new work for the dental providers. The insights will then be used to adapt the customized EHR protocols and related workflows and will be validated in a follow-up group meeting at each site where the adapted EHR screens will be presented and assessed according to the IOF implementation outcome measures of acceptability and adoption. During these follow-up meetings, we will identify any additional workflow variations that the EHR protocols may need to support. Candidate workflows will then be discussed with the project team and other non-patient participants to finalize the adapted workflow integration approach.

8.1.2 Pilot testing and live usability for remote EHR

Pilot testing and live-usability: In order to account for real world conditions, the intervention will be pilot tested at 3 Chinese American outreach sites. Early formative observations / short interviews will be conducted with dental teams at each of the pilot sites regarding interaction with the customized EHR. This pilot testing will examine impact on workflow, uncover any new usability problems, and identify any educational needs to be included before large-scale implementation. As providers at the pilot sites engage with the EHR, live-usability testing will be conducted, consisting of direct observations by the research team. Live usability is ideal for observing the impact of new tools on real setting workflows and for observing alternative workflows that can be missed during simulations.

8.1.3 Semi-structured interviews regarding the remote EHR and partnered intervention

Semi-structured interviews will be conducted with participating dentists, CHWs and other non-patient participants in administrative and technical roles after the intervention. We anticipate conducting approximately 20 interviews before obtaining data saturation. The interviews will be informed by the Consolidated Framework for Implementation Research (CFIR) and Implementation Outcomes Framework (IOF) constructs and will assess specific barriers to sustaining the partnered intervention and strategies for addressing those barriers to facilitate integration of the intervention into the routine workflow of the NYU Dentistry Local Community Outreach Programs.

In addition to survey questions, acceptability will also be assessed using open-ended questions, such as:

- Please tell us what you liked most about the program.
 - Please tell us what you did not like about the program.
 - Please tell us what changes can be made to improve the program.
 - Overall program satisfaction (scale of 1-10 answer range)
 - How did you feel about the topics covered?
-

- How did you feel about the length of time of the dental screening and oral health promotion demonstrations?

Feasibility will be assessed among the dentists, CHWs, NYU administrators, and site directors at the 3 partnering organizations. The following questions will be asked:

- How did you feel about the intake procedures?
- How did you feel about the oral health demonstrations by CHWs?
- How did you feel about the length of time of each dental screening?

8.1.4 Participatory modeling of non-patient participant knowledge

The third aim of this study is to model knowledge held by non-patient participants about factors that influence access to oral health care and care-seeking behaviors among low-income, urban Chinese American adults. This information will be used in designing simulation models at multiple levels, from multiple perspectives. A systems science approach will be undertaken to integrate knowledge held by non-patient participants into simulation models to explore alternative paths toward improved health and health care for low-income, urban Chinese American adults via community-based outreach followed by clinical care. These simulation models will be designed using a multi-method approach, in which principles of system dynamics (SD) are used to incorporate feedback effects and delays through stocks that accumulate flows (rates of change over time). The SD approach will be integrated with an agent-based modeling (ABM) framework that is used to appropriately represent dynamics at the community, site, provider, family, and patient levels. The model platform developed for this study will contain multiple model structures that characterize different dynamics and reflect participant input.

Modeling to anticipate effects of interventions. The models in this platform will simulate implications of hypotheses elicited *a priori* (before implementation of the partnered intervention) from non-patient participants. The *a priori* model platform will enable comparison to models that are later developed with hindsight from implementation of the remote EHR and partnered interventions. This model platform will therefore test the relative effectiveness of the interventions as anticipated under these *a priori* assumptions. Toward this end, this effort will involve design of scoping models that establish a baseline for simulating access at the community level and care-seeking behaviors at the individual level.

A participatory SD modeling process will be undertaken via a group model-building workshop held with non-patient participants as well as semi-structured interviews with individual non-patient participants to elicit targeted model input and feedback on assumptions. The UB Geography Systems Science Modeling Team will work closely with non-patient participants to devise indices for input parameters and indicators for outcomes of simulation experiments. In addition to informing the design of model structures, this participatory approach will enable non-patient participants to better

assess the results of the simulation models developed in this *a priori* model platform for authenticity and identification of insights for subsequent implementation research. The resulting model platform will establish a multi-level agent-based GIS framework for simulation modeling of access to oral health care and care-seeking behaviors by low-income, urban Chinese American adults at the community, site, provider, family, and patient levels.

9 ASSESSMENT OF SAFETY

9.1 Specification of Safety Parameters

Safety monitoring for this study will focus on unanticipated problems involving risks to subjects, including unanticipated problems that meet the definition of a serious adverse event.

9.1.1 *Unanticipated Problems*

The Office for Human Research Protections (OHRP) considers unanticipated problems involving risks to subjects or others to include, in general, any incident, experience, or outcome that meets **all** of the following criteria:

- unexpected in terms of nature, severity, or frequency given (a) the research procedures that are described in the protocol-related documents, such as the IRB-approved research protocol and informed consent document; and (b) the characteristics of the subject population being studied;
- related or possibly related to participation in the research (“possibly related” means there is a reasonable possibility that the incident, experience, or outcome may have been caused by the procedures involved in the research); and
- suggests that the research places subjects or others at a greater risk of harm (including physical, psychological, economic, or social harm) than was previously known or recognized.

9.1.2 *Unanticipated Problem Reporting to IRB and NIDCR*

Incidents or events that meet the OHRP criteria for unanticipated problems require the creation and completion of an unanticipated problem report form. OHRP recommends that investigators include the following information when reporting an adverse event, or any other incident, experience, or outcome as an unanticipated problem to the IRB:

- appropriate identifying information for the research protocol, such as the title, investigator’s name, and the IRB project number;
 - a detailed description of the adverse event, incident, experience, or outcome;
 - an explanation of the basis for determining that the adverse event, incident, experience, or outcome represents an unanticipated problem;
 - a description of any changes to the protocol or other corrective actions that have been taken or are proposed in response to the unanticipated problem.
-

To satisfy the requirement for prompt reporting, unanticipated problems will be reported using the following timeline:

- Unanticipated problems that are serious adverse events will be reported to the IRB and to NIDCR within 1 week of the investigator becoming aware of the event.
- Any other unanticipated problem will be reported to the IRB and to NIDCR within 2 weeks of the investigator becoming aware of the problem.
- All unanticipated problems should be reported to appropriate institutional officials (as required by an institution's written reporting procedures), the supporting agency head (or designee), and OHRP within one month of the IRB's receipt of the report of the problem from the investigator.

All unanticipated problems will be reported to NIDCR's centralized reporting system via Rho Product Safety:

- Product Safety Fax Line (US): [name]
- Product Safety Fax Line (International): [contact]
- Product Safety Email: [contact]

General questions about SAE reporting can be directed to the Rho Product Safety Help Line (available 8:00AM – 5:00PM Eastern Time):

- US: [name]
- International: [contact]

9.2 Halting Rules

This study includes no halting rules.

10 STUDY OVERSIGHT

[name] as the Lead Principal Investigator is responsible for study oversight, in collaboration with the NIDCR Program Official.

11 CLINICAL SITE MONITORING

Not applicable.

12 STATISTICAL AND EVALUATIVE CONSIDERATIONS

12.1 Study Hypotheses

Primary: Based on exit interviews, patient participants in the program will be satisfied with the partnered intervention components.

12.2 Sample Size Considerations

No formal sample size estimates were performed for this F & A study. The bar for success for both feasibility and acceptability is 80% of enrolled patient participants report being satisfied or very satisfied with the partnered intervention components.

12.3 Planned Interim Analyses (if applicable)

Because this is a feasibility study, there will be interim reviews of interview data in order to modify aspects of the partnered intervention and the remote EHR processes during the course of the study.

12.3.1 Safety Review

Not applicable.

12.3.2 Efficacy Review

Not applicable.

12.4 Final Analysis Plan

Acceptability of the partnered intervention will be assessed through exit interviews of the interview patient participants.

As we did with the Sikh American project, we will utilize a pre-post retrospective evaluation design. In this format, all questions will be asked in a single exit interview, but where applicable, will use the phrasing, "Prior to the beginning of the program..." followed by, "At the present time..." Table 3 lists the questions/domains we will use, and expected % changes we hypothesize we will observe in the current study. The percent change from pre-post will be compared using t-tests for proportions. Given that many of the answer choices are non-binary, we will also compare the shift of responses from pre-post across the categories of response using chi-squared tests. Note that this is not an exhaustive list of questions that will be asked; we are simply highlighting those questions that we will use to quantify acceptability. The full planned questionnaire is attached.

Health care utilization and oral health promotion measures: Our ultimate health care utilization measure of interest is receipt of a dental visit within the last 12 months. This will be measured using the Medical Expenditure Panel Survey (MEPS) definition, where dental visit refers to care by or visits to any type of dental provider. This will allow for

direct comparison with Healthy People 2020 Leading Health Indicator OH-7 to increase the proportion of children, adolescents, and adults who used the oral health care system in the past year.

Our central oral health promotion measure is self-reported brushing of teeth for 2 minutes twice a day with a soft-bristled toothbrush and fluoride toothpaste at the interview patient participant's 1 month follow-up visit. For the primary health care utilization measure of receipt of a dental visit within the last 12 months, we will also access the NYU Dentistry EHR database and follow-up with oral health care providers identified by participants in HIPAA approved procedures to ascertain receipt of a dental visit in the last 12 months.

Table 3 provides the measures and definitions of the oral health promotion, self-efficacy, and acceptability measures used in our prior research with the Sikh American community that will be adapted for the present F & A study with the Chinese American community.

Table 3. Measures and definitions of oral health promotion, self-efficacy, and acceptability measures

Question/Domain	Observed Change in Sikh American Project	Expected Absolute Percent Change	Expected Relative Percent Change*
How often do you brush your teeth for at least two minutes?	Increase from 17.9% to 64.7% of those reporting "More than once a day"	+45%	+261%
How often do you floss?	Increase from 4.4% to 22.1% of those reporting "More than once a day"	+20%	+400%
How confident... a) are you that you know how to take good care of your mouth, teeth, and gums? b) do you feel asking your dentist or oral hygienist questions?	a) Increase from 0% to 65.7% of those reporting "Very confident" b) Increase from 7.4% to 75% of those reporting "Very confident"	a) +65% b) +65%	a) +6500% b) +864%
Agreement with the following statements: a) CHW answered my concerns and questions b) CHW helped me to improve how I take care of my health c) Information and topics were informative d) In-person demonstrations helpful in improving oral health	Reported "Strongly Agree" a) 57.4% b) 60.3% c) 69.1% d) 76.1%	N/A	N/A

**We additionally list relative percent change in the case that baseline behaviors among the Chinese American community are very different from the Sikh American community.*

The threshold for success for acceptability of the partnered intervention will be that 80% or more of interview patient participants rate all 4 acceptability questions as agree or strongly agree.

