7.2 Outreach Center Activities

- Health Insurance Portability and Accountability Act (HIPAA) certified research staff members or volunteers will explain the consent form, confidentiality agreement, and liability release to each potential patient participant and obtain her/his signature
- Remote EHR Data Collection and Dental Screening:

-
- Authorized NYU Dentistry personnel will directly enter the demographic information of patient participants into the customized EHR using the study-specific SCREENING option
 - EHR patient participants will complete a short paper intake form that will be scanned directly into a designated SCREENING folder in the EHR regarding medical conditions that could affect, or be affected by, their oral health (Yes / No checklist) and a brief questionnaire on self-reported receipt of a dental visit in the past year and dental hygiene behaviors (Oral Health Survey). These questions will be based on the World Health Organization (WHO) Oral Health Questionnaire for Adults: (1) How often do you clean your teeth? (Never, Once a month, 2-3 times a month, Once a week, 2-6 times a week, Once a day, Twice or more a day); (2) Do you use any of the following to clean your teeth? (Toothbrush, Wooden toothpicks, Plastic toothpicks, Thread (dental floss), Charcoal, Chewstick / miswak, Other (Please specify)); (3) For those who nominate Toothbrush: What type of toothbrush do you use? (Hard-bristled, Medium-bristled, Soft-bristled) (4) Do you use toothpaste to clean your teeth? (5) For those who nominate Toothpaste, Do you use a toothpaste that contains fluoride? Correct responses to all 5 questions will indicate that EHR patient participants are following the guidance of the American Dental Association (ADA) on brushing with fluoride toothpaste. These measures will be collected in person via self-report to ascertain baseline status at the beginning of each screening event and scanned directly into the NYU Dentistry remote EHR customized for community outreach events.
 - An NYU Dentistry faculty dentist will conduct a head and neck / oral examination on each EHR patient participant and directly enter the results into the customized EHR
- The dentist will review the examination results with the EHR patient participant using a customized walkout statement with screening results and follow-up notes and answer any questions regarding oral health concerns

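### Section 12.4 tests change in brushing and flossing habits within one exit interview, apparently at the outreach visit, and states no comparison of the baseline and 1-month data that the protocol collects

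*Combined protocol and SAP*

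**What the plan says.** Section 12.4 adopts the retrospective pre-post format of the prior Sikh American project. Participants answer once about the time before the program and once about now, and "all questions will be asked in a single exit interview". On testing, it says "The percent change from pre-post will be compared using t-tests for proportions", and for items with several categories "we will also compare the shift of responses from pre-post across the categories of response using chi-squared tests". Table 3 includes brushing for at least two minutes and flossing frequency. Its +45 and +20 points are described as "expected % changes we hypothesize we will observe in the current study".

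The same section names a different behaviour measure as central, taken at the 1-month follow-up: "self-reported brushing of teeth for 2 minutes twice a day with a soft-bristled toothbrush and fluoride toothpaste". It gives no comparator, test or estimate for that measure.

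Baseline data exist. Section 8.1.1 refers to "baseline oral health measures of self-reported receipt of a dental visit in the past year and brushing with fluoride toothpaste as recommended". Section 7.2 collects the Oral Health Survey at the start of each screening event, and its first item is "How often do you clean your teeth". At about 1 month, section 7.3 has the CHW ask about brushing frequency and fluoride toothpaste.

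**The concern.** The exit interview appears to take place minutes or hours after the demonstration. A participant asked then how often he or she brushes or flosses at present has no new habit to report. The answer can differ from the before-program answer because of intention, a revised view of past behaviour, or the pairing of the two questions. A significance test on that difference looks like evidence of behaviour change and is not.

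Section 3 says the study is meant to inform a larger randomised trial. A significant exit result, at or near the hypothesised +45 or +20, could be carried into that trial as a behavioural effect. The contacts better placed to detect change, baseline and 1 month, have no stated comparison.

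**Working it through.** **When the exit interview takes place**

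- Special Terms (Patient Participants) places it after the intervention, at the outreach centers.
- The Protocol Summary gives each interview participant one in-person visit and one telephone follow-up.
- Section 7.2 lists it under outreach center activities, directly after the CHW demonstration, and has the dental voucher given out there.
- Section 7.3 puts the CHW follow-up at about 1 month, with a window of -7 days to +1 month. That is roughly day 30 - 7 = 23 to day 30 + 31 = 61.
- Table 2 names exit and 1-month interviews as separate contacts.

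Together these point to the outreach visit. None states the day.

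**The plan's own figures**

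- Interview sample (section 5.1): 0.60 x 150 = 90. This reproduces.
- Table 3, prior project, brushing: 64.7 - 17.9 = 46.8 points, against a stated expectation of +45.
- Table 3, prior project, flossing: 22.1 - 4.4 = 17.7 points, against +20.
- In patients: 0.45 x 90 = 40.5 and 0.20 x 90 = 18.

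**How few altered answers make the exit test positive**

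Inputs: n = 90; baselines assumed equal to the prior project's, so 0.179 x 90 = 16 for brushing and 0.044 x 90 = 4 for flossing; two-sided 5% level, assumed because 12.4 gives none. Section 12.4 does not say whether its test is paired.

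Unpaired test, no continuity correction: z = (p2 - p1) / sqrt(2p(1 - p)/n), with p the pooled proportion.

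- Brushing, 16 against 28: p = 44/180 = 0.244, z = 0.1333/0.0641 = 2.08, p-value 0.037. With 27 instead of 28 the p-value is 0.055.
- Flossing, 4 against 12: p = 16/180 = 0.089, z = 0.0889/0.0424 = 2.10, p-value 0.036. With 11 the p-value is 0.059.

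So 12 of 90 (13%) or 8 of 90 (9%) more favourable answers suffice, with no habit changed. An exact paired test needs 6 of 90 with none in reverse: 2 x 0.5^6 = 0.031.

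**Which items could be compared prospectively**

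| Item | Baseline (7.2) | 1 month (7.3) |
|---|---|---|
| Cleaning/brushing frequency | listed | listed |
| Fluoride toothpaste use | listed | listed |
| Bristle type | listed | not named |
| Two-minute duration | not listed | not listed |
| Flossing frequency | not listed | not listed |

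Floss appears at baseline only as a cleaning aid, without frequency.

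**Precision of the paired comparison**

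Let b be the share that improves, c the share that shifts in reverse, and d = b - c. Then SE = sqrt((b + c - d²)/n), where b + c = d + 2c, and the 95% half-width is 1.96 x SE. The documents give no expected change for the two shared items, so d and c are assumptions. At n = 90:

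| d | c = 0 | c = 5% | c = 10% |
|---|---|---|---|
| 10 points | 6.2 | 9.0 | 11.1 |
| 20 points | 8.3 | 10.5 | 12.4 |

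Example: d = 0.10, c = 0.05 gives sqrt((0.20 - 0.01)/90) = 0.0459, and 1.96 x 0.0459 = 0.090.

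**The case against.** The strongest reply is that nothing depends on these tests. The only hypothesis in 12.1 is satisfaction. The 12.4 success rule is 80% of interviewees agreeing or strongly agreeing with four statements, and 12.4 presents the Table 3 questions as a way to quantify acceptability. That stands and limits the severity. A reader might infer that the study's success criterion is compromised. It is not, because the rule does not use the brushing or flossing items.

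Second, same-visit timing is inferred. CHW follow-up is itself component 4 of the intervention, so an interview after the intervention could in principle come later, and section 7.3 allows the follow-up in person. This stands as a caveat. If the exit interview were held weeks later, the argument that no habit could have changed would fall away. The missing comparison would remain.

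Third, the replacement has biases of its own. It is uncontrolled self-report, moves from an intake form to a CHW contact, and takes answers given to the CHW who taught the behaviour. The listed wording also differs: cleaning at baseline, brushing at 1 month. All of this stands. A reader might infer that the paired change would show an effect of the intervention, and it could not. Its advantage is narrower: the second answer comes after time in which a habit could change.

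Fourth, the retrospective format was chosen to match the prior project. Keeping the exit pair as a descriptive result preserves most of that.

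A reader might also infer that the forms lack two-minute brushing or flossing frequency. The documents do not support this: "The full planned questionnaire is attached", and the form is not in the available text.

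**Conclusion.** The point holds, at the low end of should-fix. As written, 12.4 tests change in two habits from paired answers in one interview that most naturally falls just after the demonstration, and it states no comparison of the baseline and 1-month data. Under the assumptions above, a significant exit result needs only 12 altered brushing answers or 8 altered flossing answers out of 90, against hypothesised shifts of about 40 and 18.

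The half-widths for the proposed analysis are illustrations. They describe neither two-minute brushing nor flossing, so they are not power statements about +45 or +20. They take the 90 as responders at 1 month because section 5.1 expects that group to complete both interviews. With fewer responders they widen in proportion to 1/sqrt(n).

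A related limit of scope is that the exit-based primary outcome precedes CHW follow-up, so it cannot cover patients' experience of that component. This needs a clarifying sentence and does not invalidate the outcome.

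**What to change.** **Main change, in 12.4.** Make the paired baseline-to-1-month change the behaviour analysis, for the two items listed at both contacts: cleaning or brushing at least twice a day, and use of fluoride toothpaste. Word each item the same both times. Report an estimate with a 95% CI and the number of 1-month responders. Report the exit brushing and flossing pair descriptively, for comparability with the prior project, without a test of change. Keep the retrospective pair for the two confidence items, which can change within a visit.

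**Clarifications.** State in 7.2 whether the exit interview is on the screening day. State in 3.2.1 that exit satisfaction precedes, and so does not cover, CHW follow-up.

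**Optional.** Check the attached forms. If they lack them, two-minute brushing and flossing frequency could be added at both contacts and bristle type at 1 month. The upper bound is 2 x 150 + 3 x 90 = 570 extra answers, probably with translation and community advisory board review.

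**Cost.** The main change and clarifications add no items. They need edits to 3.2.1, 7.2 and 12.4, aligned item wording on the forms, and the IRB approval that 15.2 requires for any amendment. The downsides are 1-month non-response, a probably smaller observed change, the change of mode with answers given to the CHW, and less comparability with the prior project.

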4 STUDY DESIGN

This feasibility and acceptability study will be conducted at 3 community outreach centers serving an urban, low-income Chinese American population. The study will evaluate the feasibility and acceptability of implementing a partnered intervention to improve the oral and general health of low-income, urban Chinese American adults and of using remote entry into an electronic health record (EHR). The evaluation will include group adaptation sessions and workflow analyses of the EHR implementation, involving multiple recorded sessions with NYU administrators, providers (dentists and CHWs), outreach site directors, and research staff. The study will also model *a priori* knowledge held by non-patient participants to evaluate and enhance the intervention during and/or after the study for use in future implementations.

Approximately 50 patient participants who self-identify as Chinese American from each of 3 center (n = 150) will be consented to allow the entry of their data (e.g., demographic information, medical history, receipt of oral health care visits, dental hygiene behaviors, and health and health care measures) into the remote EHR by authorized NYU Dentistry staff (EHR patient participants). Of these 150 EHR patient participants, research staff will survey approximately 30 Chinese American patient participants from each of 3 outreach centers (n = 90) regarding their satisfaction with the intervention components (interview patient participants). The study team will also evaluate feedback from approximately 32 non-patient participants selected from the following groups: research staff, CAB members, outreach site directors, NYU administrators, and providers (dentists and CHWs); these individuals will be interviewed about various aspects of the partnered intervention and/or the remote EHR implementation process and/or their *a priori* knowledge of factors that influence access to oral health care and care-seeking behaviors among low-income, urban Chinese American adults.

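### The chi-squared test of the pre-post shift ignores the order of the answer categories, so it cannot separate improvement from worsening; minor, and fixed by one sentence in Section 12.4

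*Combined protocol and SAP*

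**What the plan says.** Section 12.4 sets out a retrospective pre-post design: "all questions will be asked in a single exit interview", with each applicable item answered once for the time before the program and once for the present. Two analyses follow. The first is on a proportion: "The percent change from pre-post will be compared using t-tests for proportions". The second is added because a number of items have more than two possible answers, which a single proportion does not use in full. Its wording is: "we will also compare the shift of responses from pre-post across the categories of response using chi-squared tests".

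Table 3 in the same section shows which items carry a pre-post change. One is "How often do you brush your teeth for at least two minutes"; the others are flossing frequency and two confidence questions. The reported category in each case is the top of an ordered scale (more than once daily, or very confident), and every expected change is positive: +45 points for brushing, +20 for flossing, +65 for each confidence item. The four agreement statements have no pre-post change.

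Section 12.4 gives no category scores, no trend version of the chi-squared test, no paired version, no directional summary and no significance level.

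**The concern.** A shift in how often people brush, or in how confident they feel, is movement along an ordered scale. An ordinary chi-squared test treats the categories as unordered labels and asks only whether the two distributions differ in some way. Three things follow.

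- A significant result does not say that answers moved up.
- Equal movement in both directions can produce significance.
- The test spreads its power over several degrees of freedom, so a modest, graded improvement is harder to detect.

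Making the test paired does not cure this by itself, because the usual paired versions (Bowker, Stuart-Maxwell) also ignore order. What is at stake is how the behaviour and confidence results are read. Section 3 says the study is meant to inform the design of a larger randomised trial, so a misread shift could carry forward.

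**Working it through.** **Inputs from the documents.** About 90 exit interviews, 30 at each of 3 centers (Section 4). Pre and post answers come from the same person (Section 12.4). Items and expected changes are from Table 3. The plan gives no sample size calculation (Section 12.2) and no power for this test, so there is no figure to reproduce.

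**Assumptions.** Two-sided 5% level; 4 or 5 categories; the category distributions shown below. The documents give none of these for the exit-interview items.

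**1. Significant with no net movement.** For two distributions of equal size, Pearson's statistic is the sum over categories of (before − after)² / (before + after).

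| Category score | 0 | 1 | 2 | 3 | Mean |
|---|---|---|---|---|---|
| Before | 10 | 35 | 35 | 10 | 135/90 = 1.5 |
| After | 20 | 25 | 25 | 20 | 135/90 = 1.5 |
| Contribution | 100/30 | 100/60 | 100/60 | 100/30 | |

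X² = 3.33 + 1.67 + 1.67 + 3.33 = 10.0 on 3 df, p = 0.019. The mean is unchanged.

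**2. Pairing alone does not help.** Let the same margins arise from 10 patients falling one step (score 1 to 0), 10 rising one step (score 2 to 3), and 70 unchanged. Stuart-Maxwell splits into two independent pieces, each 10²/10 = 10, so the statistic is 20.0. The covariance matrix has rank 2 here, so the reference is 2 df: p = 0.00005. Wilcoxon signed-rank, with 10 equal rises against 10 equal falls, gives p = 1.0.

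**3. Blind to direction.** Take 18/18/18/18/18 before and 9/13/18/22/28 after. X² = 81/27 + 25/31 + 0 + 16/40 + 100/46 = 3.00 + 0.81 + 0 + 0.40 + 2.17 = 6.38 on 4 df, p = 0.17. The mirror-image worsening, 28/22/18/13/9, gives the same 6.38 and the same p. A 1-df linear-trend test on the same counts gives 6.26, p = 0.012, and its sign shows the direction.

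**4. Power for graded shifts.** Simulation with n = 90, 5 categories and baseline 15/25/30/20/10%; each patient moves up one step, down one step or stays.

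| Up / down | Stuart-Maxwell | Signed-rank |
|---|---|---|
| 30% / 12% | about 59% | about 77% |
| 20% / 8% | about 36% | about 61% |
| 30% / 0% | 100% | 100% |
| 20% / 0% | about 99% | 100% |
| 12% / 0% | about 63% | about 99% |

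A different model (correlated normal variables cut into 5 equal categories, correlation 0.5) agrees. For shifts of 0.2, 0.3, 0.4 and 0.5 SD, Stuart-Maxwell has 22, 47, 76 and 93% power, against 39, 72, 92 and 99% for a paired ordered score test. Unpaired Pearson has 9, 22, 48 and 74%, but part of that loss comes from ignoring the pairing: with no true change at this correlation it rejects only 2.5% of the time.

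**5. Where the power loss disappears.** At the Table 3 brushing and confidence effects, every test examined has about 100% power. For flossing (4.4% plus 20 points), if only the top category gains and the others shrink evenly, Pearson has 92% to 93%, against 70% to 91% for the paired ordered score test. There the unordered test does as well or better.

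**The case against.** The strongest reply is that little depends on this test. The primary outcome is patient satisfaction (Section 3.2.1). The 80% bars in Sections 12.2 and 12.4 rest on satisfaction and on the four agreement statements, not on any pre-post item. The shift test is an addition to the comparison of proportions, which does show direction. All of this stands and sets the priority. The proportion comparison looks at one cut-point only, however. In the first worked example the top category rises from 10 to 20 although there is no net movement, so the two tests could both point the wrong way.

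A second reply is that balanced up-and-down movement is unlikely when both answers are given in one interview after a demonstration, and that the earlier project saw large rises (for brushing, "Increase from 17.9% to 64.7% of those reporting" the top answer). That is fair: the example shows what the test can do and is not a forecast. Nor should a reader infer that real upward shifts will generally be missed. With few or no downward moves, or with effects near most of Table 3, both kinds of test succeed. Smaller shifts remain possible, since the Table 3 footnote allows that baseline behaviour in this community may be very different.

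A third reply is that the type of chi-squared test is not named, and a linear-trend version would use order. That is true, but nothing in Section 12.4 points to one. The questionnaire, which is said to be attached, was not available, so the number of categories is assumed.

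**Conclusion.** The point holds as a minor one. As written, the shift test does not use the order of the answers, cannot tell improvement from worsening, and can be significant with no net movement (X² = 10.0, p = 0.019 in the example). These properties belong to any unordered test and do not depend on the assumed distributions.

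The loss of power does depend on them. It is roughly 18 points (59% against 77%) and 25 points (36% against 61%) in the two mixed-direction scenarios, and absent at effects as large as most of Table 3 or when the gain is confined to the top category.

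A reader might infer that the study's acceptability conclusion is at risk, or that direction is never examined. The documents support neither: the success thresholds do not use this test, and the proportion comparison gives direction at one cut-point.

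**What to change.** In Section 12.4, replace the chi-squared shift test with a paired test that uses category order, for example Wilcoxon signed-rank on each patient's change. Keep a pre-post comparison of the top-category proportion, which covers the case where only that category gains. For each item, report the numbers who moved up, stayed and moved down.

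This costs one sentence and needs no new data. Because the test works on each patient's own change, the same sentence also deals with the pairing of the answers for the shift analysis. The downside is less sensitivity to change that is not in one direction; the up/same/down counts would still show it.
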